5.3.3 Safety laboratory parameters

The laboratory tests listed in [Table 5.3.3: 1](#) will be performed at the central laboratory service provider. Local laboratory may be used for selected tests in exceptional cases. Patients should be fasting for at least 8 hours prior to the blood sample being taken (except Screening Visit).

Instructions regarding sample collection, sample handling/ processing and sample shipping are provided in the Laboratory Manual in the ISF. For time points of laboratory sampling, see [Flow Chart](#).

Laboratory results (i.e. all safety laboratory and clinical laboratory data relevant for current clinical practice) of the patients will be available in real time to the respective investigator (via laboratory reports) and to the sponsor (via the central laboratory website) and selected abnormal laboratory alerts will be flagged to the site and sent to sponsor in real time.

Clinically relevant abnormal findings will be reported as baseline conditions or AEs. A clinically relevant value may be either in- or outside the reference range. Clinically relevant abnormal laboratory test results must be confirmed using an unscheduled visit laboratory kit and should be repeated until normalization or stabilization or until an alternative explanation has been found. Abnormal laboratory values will be also graded for intensity by using RCTC Version 2.0 criteria ([R13-3515](#)).

Table 5.3.3: 1 Laboratory tests

Category	Test name
Haematology	Hematocrit (Hct) Hemoglobin (Hb) Glycosylated Hbc (HbA1c) Red Blood Cell Count/ Erythrocytes Reticulocyte Count White Blood Cells / Leukocytes Platelet Count/ Thrombocytes
Diff. Automatic	Neutrophils (relative and absolute count) Eosinophils (relative and absolute count) Basophils (relative and absolute count) Monocytes (relative and absolute count) Lymphocytes (relative and absolute count)
Diff. Manual (if Diff Automatic is abnormal)	Neutrophils, bands (Stabs) Neutrophils, polymorphonuclear (PMN) Eosinophils Basophils Monocytes Lymphocytes
Coagulation	Activated Partial Thromboplastin Time (aPTT) Prothrombin time (INR) Fibrinogen

Table 5.3.3: 1 Laboratory tests (cont'd)

Category	Test name
Enzymes	AST(GOT) ALT(GPT) Alkaline Phosphatase (AP) Creatine Kinase (CK) CK-MB, only if CK is elevated Gamma-Glutamyl Transferase (GGT/ γ -GT) Lactic Dehydrogenase (LDH) Amylase Lipase
Electrolytes	Calcium Sodium Potassium Chloride Bicarbonate
Substrates	Glucose BUN (blood urea nitrogen) Uric acid Creatinine eGFR (estimated by CKD-EPI formula) Bilirubin Total Bilirubin Direct (if total is elevated) Bilirubin Indirect (if total is elevated) Troponin I (reflex when CK is elevated) Albumin C-Reactive Protein (high sensitive) Cholesterol, total Triglycerides LDL-Cholesterol (calculated by Friedewald formula) HDL-Cholesterol HOMA-IR (only at Visit 2, Visit 8, and EOT Visit)
Urine Pregnancy test (only for female patients of childbearing potential) at randomization and continued as indicated in the Flow Chart (including EOT and EOO Visit) (test done in clinic)	Human Chorionic Gonadotropin in the urine (Dipstick not performed at central lab)
Serum Pregnancy test (only for female patients of childbearing potential) at screening and if urine pregnancy test is positive)	Human Serum Chorionic Gonadotropin (quantitative)
Hormones (only at screening)	TSH, (free T3 and free T4 in case of abnormal TSH results)

Table 5.3.3: 1 Laboratory tests (cont'd)

Category	Test name
Autoantibodies (only at screening)	Rheumatoid Factor
Urinalysis (dipstick)	Urine Nitrite Urine Protein Urine Glucose Urine Ketone Urobilinogen Urine Bilirubin Urine RBC/ Erythrocytes Urine WBC/ Leukocytes Urine pH
Urine-Sediment (microscopic examination, only if urine analysis abnormal)	Urine Sediment Bacteria Urine Cast in Sediment Urine Squamous Epithelial Cells Urine Sed. Crys., Unspecified Urine Sediment RBC/ Erythrocytes Urine Sediment WBC/ Leucocytes
Urine	Albumin (quantitative) Creatinine Albumin/creatinine ratio
Infections screening (only at screening and EOT Visit)	Hepatitis B Surface Antigen (qualitative) Hepatitis C Antibodies (qualitative) HIV-1, and HIV-2 Antibody (qualitative) QuantiFERON®-TB ¹

¹ There is the trial site option to perform a PPD skin test, although this will not be provided or performed at Central Lab.

5.3.4 Electrocardiogram

The 12-lead ECGs will be performed as scheduled in the [Flow Chart](#).

ECGs will be recorded after the patients have rested for at least 5 minutes in a supine position and will always precede blood sampling. Six limb leads, as specified by Einthoven (I, II and III) and Goldberger (aVR, aVL, aVF), and six pre-cordial leads (V1–V6), according to Wilson, will be used.

ECGs may be repeated for quality reasons and the repeat used for analysis. Additional ECGs may be collected for safety reasons. Clinically relevant, abnormal findings will be reported as AEs.

Information about the details of ECG collection and the parameters assessed will be provided in the ISF.

ECGs will be read and evaluated by a central vendor. The study site will be informed about the results of the assessment of the ECG obtained at screening and if there are findings that would exclude the patient from study participation according to exclusion criterion #9.

The electronic version of the ECG is regarded as source data. Dated and signed printouts will be stored in the patient's medical file.

5.3.5 Other safety parameters

Local tolerability at the administration site of the subcutaneous injection will be assessed by the investigator according to "swelling", "induration", "heat", "redness", "pain", or "other findings" at the specified visits as noted in the [Flow Chart](#). This assessment should be done pre-dose.

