Local tolerability ¹⁰			X	X	X			X			X				X	

Trial Periods	Screen- ing	Randomized Treatment														FU
Visit	V1	V2	V3	V4	V5	V6	V7	V8	V9	V10	V11	V12	V13	V14	EOT	EOO
Week			1	3	4	8	12	16	20	24	28	32	36	40	44	EOT +4 ¹⁸
Day	-42 to -7	1	8	22	29	57	85	113	141	169	197	225	253	281	309	EOT +28 ¹⁸
Visit window (days)			±1	±3	±3	±3	±3	±3	±3	±3	±3	±3	±3	±3	±3	±7
PASI / sPGA	X	X			X	X	X	X	X	X	X	X	X	X	X	
NAPSI / PPASI / PSSI		X						X							X	
DLQI and WLQ		X						X							X	
HCRU ¹¹		X			X	X	X	X	X	X	X	X	X	X	X	
Optional skin biopsy ^{1,12}		X					X									
Optional DNA banking ^{1,13}		X														
Randomization, Re-Randomisation ¹⁴		X						X ¹⁴								
Contact IRT	X	X	X	X	X	X	X	X	X	X	X	X	X	X	X	
Administration of trial drugs at study visits ¹⁵		X	X	X	X			X	X		X	X				
Self administration questionnaire for Study Drug BI 655066 (active or placebo) ¹⁶					X			X	X		X	X				
Dispensation of trial drugs to patient ¹⁷					X	X	X	X	X	X	X	X	X	X		
Termination of trial medication ²⁰															X	
Trial completion ¹⁸															X	X
Vital status ¹⁹																X

FOOTNOTES

1. After patients have been informed about the trial, written informed consent in accordance with ICH-GCP and the local legislation must be obtained prior to performing any study related procedures. A separate informed consent is required for optional study procedures if patients will participate in these optional study procedures which are DNA banking from blood samples, biomarker serum sample banking, skin biopsies and biomarker tissue sample banking from skin biopsies.
2. For detailed instructions how to measure waist circumference see [section 5.3.1.1](#) for waist circumference procedure.
3. Physical examination: C=complete, T=targeted. Refer to [Section 5.3.1](#).
4. Measurement of vital signs should precede blood sampling and be assessed pre-dose. Additional assessments will be done approximately 5 minutes post-dose (5 min. after last injection) and approximately 60 minutes post-dose (60 min. after last injection) at Visit 2 and Visit 5. Refer to [Section 5.3.2](#). Patients should be closely monitored for signs and symptoms of hypersensitivity reactions for approximately 2 hours after the last injection at the Randomization Visit

and for approximately 1 hour after the last injection at all other study visits with drug administrations. Hypersensitivity reactions should be treated according to medical standards.

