3. DESCRIPTION OF DESIGN AND TRIAL POPULATION

3.1 OVERALL TRIAL DESIGN AND PLAN

This confirmatory multi-national, randomized, double-blind, double dummy, active controlled, parallel design study compares BI 655066 with adalimumab. In total, approximately 600 patients with moderate to severe chronic plaque psoriasis will be randomized in this trial.

Patients are included in the study once they have signed the informed consent. Patients suitable after screening will be eligible to participate in the 44 week treatment period and will be randomized at a ratio of 1:1 to one of 2 treatment arms (BI 655066 or adalimumab) shown in [Figure 3.1: 1](#).

Patients initially randomized to BI 655066 will stay on BI 655066.

At Week 16, patients initially on adalimumab and <PASI 50 will be switched to BI 655066.

At Week 16, patients initially on adalimumab and \geq PASI 90 will stay on adalimumab.

At Week 16, patients initially on adalimumab and \geq PASI 50 and <PASI 90 will be re-randomised 1:1 to receive either BI 655066 or adalimumab.

[figure not shown]

Figure 3.1: 1 Trial design

Patients will be blinded to treatment. Patients in each dose group will receive the same injections (active or placebo) at each designated time point, in order to maintain blinding.

Patients starting and continuing with BI 655066 active drug will receive 2 syringes of BI 655066 active drug (2 x 75mg) at randomization, at Weeks 4, 16 and 28 and placebo adalimumab at randomization (2 syringes) and 1 placebo adalimumab syringe at Weeks 1, 3, 5, 7, 9, etc. up to Week 41. These patients also receive 2 syringes of BI 655066 placebo at Weeks 20 and 32 to maintain blinding to the BI 655066 active treatment arm starting at Week 16 after adalimumab pre-treatment. BI 655066 active treatment always starts with a loading dose 4 weeks after the first injection.

Patients starting with active adalimumab and switching to active BI 655066 at Week 16 will receive 2 syringes active adalimumab at randomization (2 x 40mg) followed by 1 syringe active adalimumab (40mg) at Weeks 1, 3, 5, 7, 9, 11, 13, 15; and 1 placebo adalimumab syringe at Weeks 17, 19, 21, etc. up to Week 41 to maintain blinding. These patients also receive 2 syringes of BI 655066 placebo at randomization and Week 4 followed by two active BI 655066 injections (2 x 75mg) at Weeks 16, 20 and 32 as well as 2 placebo BI 655066 injections at Week 28.

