5.3.2 Vital Signs

Vital signs evaluations will be performed at visits as shown in the [flow chart](#). This includes temperature, pulse rate, systolic/diastolic blood pressure and respiratory rate. Respiratory rate, pulse rate, and blood pressure will be measured after patients have been sitting comfortably for at least five minutes. Measurement of vital signs should precede blood sampling to avoid the impact of blood sampling on the vital measurements. At dosing visits vital signs evaluations will be performed pre-dose and at Visit 2 and Visit 5 additional measurements will be performed approximately 5 minutes post-dose (5 min. after last injection) and approximately 60 minutes post-dose (60 min. after last injection).

Patients should be closely monitored for signs and symptoms of hypersensitivity reactions for approximately 2 hours after the last injection at the Randomization Visit and for approximately 1 hour after the last injection at all other visits with drug administration. Hypersensitivity reactions should be treated according to medical standards. Pre-medications for further injections might be considered and will be agreed on between investigator and BI clinical monitor.

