4.2 Design Diagram

This confirmatory multi-national, randomized, double-blind, double dummy, active controlled, parallel design study compares risankizumab with adalimumab. In total, approximately 600 subjects with moderate to severe chronic plaque psoriasis will be randomized in this trial.

Subjects are included in the study once they have signed the informed consent. Subjects suitable after screening will be eligible to participate in the 44 week treatment period shown in [Figure 1](#).

Subjects will be blinded to treatment. Subjects in each dose group will receive the same injections at each designated time point, in order to maintain blinding.

Part A:

Part A is a 16-week, double-blinded, active-controlled treatment period during which subjects will be randomized at a 1:1 ratio to risankizumab or adalimumab. The randomization will be stratified by weight (≤ 100 kg vs. > 100 kg) and prior exposure to TNF antagonists (0 vs. ≥ 1). Subjects randomized to risankizumab will receive 2 syringes of risankizumab active drug (2×75 mg) at randomization and at Week 4, and adalimumab placebo at randomization (2 syringes) and 1 adalimumab placebo syringe at Weeks 1, 3, 5, 7, 9, etc. up to Week 15. Subjects randomized to adalimumab will receive 2 syringes adalimumab at randomization (2×40 mg) followed by 1 syringe adalimumab (40 mg) at Weeks 1, 3, 5, 7, 9, 11, 13 and 15. These subjects will also receive 2 syringes of risankizumab placebo at randomization and at Week 4.

Part B:

[figure not shown]
At Week 16, subjects initially on risankizumab will stay on risankizumab. These subjects will receive 2 syringes of risankizumab (2×75 mg) at Week 16 and 28, and 2 syringes of risankizumab placebo at Week 20 and 32. They will also receive 1 syringe of adalimumab placebo at Weeks 17, 19, 21, 23, etc. up to Week 41.

At Week 16, subjects initially on adalimumab and have $<$ PASI 50 response ($<$ 50% reduction in Psoriasis Area and Severity Index (PASI)) will be switched to risankizumab. These subjects will receive 2 syringes of risankizumab (2×75 mg) at Week 16, 20, and 32, and 2 syringes of risankizumab placebo at Week 28. They will also receive 1 syringe of adalimumab placebo at Weeks 17, 19, 21, 23, etc. up to Week 41.

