- b. The minimum of upper bound and first dose date of study drug on or after Week 16 (and within 105 days of last dose for safety analyses). If time is collected in vital signs, restrict to records prior to the first dose of study drug on or after Week 16.

Table 5. Visit Windows for Laboratory and ECG Parameters for Part A (Safety_A Population)

Window Label	Target Day	Time Window
Baseline	1	≤ 1
Week 4	29	[2, 71]
Week 16	113	[72, 155 ^a]

Rx Day calculated relative to the first dose date of study drug. For subjects randomized but not dosed, Rx Day calculated relative to randomization.

- a. The minimum of upper bound and first dose date/time on or after Week 16 (and within 105 days of last dose for safety analyses).

Table 6. Visit Windows for Other Efficacy Endpoints Only Collected at Week 16 in Part A (ITT_A Population)

Window Label	Target Day	Time Window
Baseline	1	≤ 1
Week 16	113	[2, 225 ^a]

Rx Day calculated relative to the first dose date of study drug. For subjects randomized but not dosed, Rx Day calculated relative to randomization.

- a. The minimum of upper bound and first dose date of study drug on or after Week 16.

Table 7. Visit Windows for Local Tolerability for Part A (Safety_A Population)

Window Label	Target Day	Time Window
Week 1	8	[2,15]
Week 3	22	[16, 25]
Week 4	29	[26, 71]
Week 16	113	[72, 155 ^a]

Rx Day calculated relative to the first dose of study drug. For subjects randomized but not dosed, Rx Day calculated relative to randomization.

- a. The minimum of upper bound and first dose date of study drug on or after Week 16 (and within 105 days of last dose for safety analyses) (and within 105 days of last dose for safety analyses). If time is collected in vital signs, restrict to records prior to the first dose of study drug on or after Week 16.

Table 8. Visit Windows for Analysis of PASI and sPGA in Part B (ITT_B_RR/ITT_B_R/ITT_B_NR/ITT_B_RZB/PP_B_RR Populations)

Window Label	Target Day	Time Window
Entry of B	1	≤ 1
Week 20	29	[2, 43]
Week 24	57	[44, 71]
Week 28	85	[72, 99]
Week 32	113	[100, 127]
Week 36	141	[128, 155]
Week 40	169	[156, 183]
Week 44	197	[184, 211]

Rx Day calculated relative to the first dose of study drug in Part B. For subjects re-randomized but not dosed in Part B, Rx Day calculated relative to the IRT date of re-randomization evaluation.

Table 9. Visit Windows for Laboratory and ECG Parameters for Part B (Safety_B_RR Population)

Window Label	Target Day	Time Window
Entry of B	1	≤ 1
Week 28	85	[2, 141]

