11.6 Local Tolerability

Local tolerability of the subcutaneous injection will be assessed by the investigator according to 6 items: swelling, induration, heat, redness, pain, and other findings. Proportion of subjects reporting each condition will be analyzed.

Analyses will be conducted in the Safety_A Population and the Safety_B_RR Population. In addition, the overall rate (with at least one occurrence) during the study will also be presented in the ALL_RZB Population.

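### Local tolerability is scored only before dosing, so every planned between-arm comparison except Week 1 inspects active risankizumab sites later than active adalimumab sites

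*Protocol*

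**What the plan says.** Protocol 5.3.5: "Local tolerability at the administration site of the subcutaneous injection will be assessed by the investigator", covering swelling, induration, heat, redness, pain and other findings. It then says "This assessment should be done pre-dose". The Flow Chart row "Local tolerability" marks Visits 3, 4, 5, 8, 11 and EOT (Weeks 1, 3, 4, 16, 28 and 44). SAP Tables 7 and 12 have analysis windows for the same weeks. No visit has a post-dose score.

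Dosing: the risankizumab arm receives "2 syringes of BI 655066 active drug (2 x 75mg) at randomization, at Weeks 4, 16 and 28" (Protocol 3.1). In Part A the adalimumab arm receives a loading dose "followed by 1 syringe adalimumab (40 mg) at Weeks 1, 3, 5, 7, 9, 11, 13 and 15" (SAP 4.2), and patients who stay on adalimumab continue every other week to Week 41. Patients switched at Week 16 receive active risankizumab at Weeks 16, 20 and 32. Each arm also receives 0.9% saline dummies of the other product (Protocol Tables 4.1.1: 2 and 4.1.1: 4).

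Analysis: SAP 11.6 says "Proportion of subjects reporting each condition will be analyzed" in Safety_A and Safety_B_RR, and adds an overall rate in ALL_RZB. SAP 11.6 names no test itself. SAP 11.1 lists local tolerability among the safety analyses, plans risankizumab v adalimumab comparisons in those two populations, and assigns Fisher's exact test to categorical variables. Protocol 7.3.4 says that no safety hypothesis testing is planned.

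**The concern.** A local reaction is visible for a limited time. An inspection made just before the next dose sees whatever is left of the reaction to the previous one. The two products have very different dosing intervals, so a common pre-dose schedule is not a common time since injection. The planned proportions are not separated by time since injection or by whether the inspected site received active drug or saline.

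Safety against adalimumab is part of the main objective (Protocol 2.2), and local tolerability is one of the tables that would support a statement on it. A difference in that table could reflect the inspection schedule and not the drugs. The single-arm rate in ALL_RZB has a related weakness: switched patients have no scheduled inspection sooner than 56 days after their most recent risankizumab dose.

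**Working it through.** **Inputs.** Scoring weeks: Flow Chart, SAP Tables 7 and 12. Dosing weeks: Protocol 3.1 and Table 4.1.4: 2, SAP 4.2.

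**Reproducing the plan's days.** Nominal day = 7 × week + 1. This gives Week 4 = Day 29 and Week 16 = Day 113 (Flow Chart, Protocol Table 4.1.4: 1), and Week 15 = Day 106 (SAP Table 19). All three match.

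**Interval** = day of inspection − day of the last active injection before it.

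| Planned comparison | Inspection | Risankizumab | Adalimumab |
|---|---|---|---|
| Safety_A | Week 1 | 8 − 1 = 7 | 8 − 1 = 7 |
| Safety_A | Week 3 | 22 − 1 = 21 | 22 − 8 = 14 |
| Safety_A | Week 4 | 29 − 1 = 28 | 29 − 22 = 7 |
| Safety_A | Week 16 | 113 − 29 = 84 | 113 − 106 = 7 |
| Safety_B_RR | Week 28 | 197 − 141 = 56 | 197 − 190 = 7 |
| Safety_B_RR | Week 44 | 309 − 225 = 84 | 309 − 288 = 21 |

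In Safety_B_RR the risankizumab column is the re-randomised group that switched. With the regular ±3-day windows on both dose and inspection, Week 16 becomes 84 ± 6 = 78-90 days against 7 ± 6 = 1-13 days. The ranges do not overlap.

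**Illustration of direction and size.** None of these assumptions comes from the documents. Each active product causes a reaction with the same probability *p* = 10%. Visibility halves every *h* days. A saline dummy causes a reaction with probability *q*. Only the most recent active and dummy injections count, and there are 300 patients per arm. At Week 16:

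- adalimumab proportion = *p* × 0.5^(7/*h*)
- risankizumab-arm proportion = 1 − (1 − *p* × 0.5^(84/*h*)) × (1 − *q* × 0.5^(7/*h*))

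The last column is the share of 1,000 simulated trials with Fisher p ≤ 0.05.

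| *h* (days) | *q* | Adalimumab | Risankizumab arm | Fisher p ≤ 0.05 |
|---|---|---|---|---|
| 14 | 0 | 7.1% | 0.2% | 100% |
| 7 | 0 | 5.0% | 0.0% | 99.7% |
| 7 | 2% | 5.0% | 1.0% | 79% |
| 7 | 5% | 5.0% | 2.5% | 27% |
| 7 | 10% | 5.0% | 5.0% | 3% |
| 2 | 0 | 0.9% | 0.0% | 5% |

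With *p* = 5% and *q* = 0, the proportions are 2.5% v 0.0% at *h* = 7 (77%) and 0.4% v 0.0% at *h* = 2 (0.2%). True rates for the two active products are equal in every row, so any difference comes from timing and the saline dummy.

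**The case against.** **The double-dummy.** At Week 16 the risankizumab arm also has a 7-day-old adalimumab-type site, so the inspector sees a recent site in both arms. This keeps the blind and narrows the gap, but in the risankizumab arm that site received saline. The imbalance disappears only if saline is as reactive as active drug.

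**Other capture.** Adverse events are collected throughout, every visit has a physical examination, and patients are observed after on-site injections ("for approximately 1 hour after the last injection at all other visits with drug administration"; about 2 hours at randomisation). Reactions can therefore be recorded as adverse events whatever the inspection schedule. This stands, and it is a reason to rest the comparative statement on adverse events. It does not repair the scheduled comparison.

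**Standing of the variable.** The protocol treats local tolerability descriptively. It is not an efficacy endpoint, and injection-site reaction is not an Area of Safety Interest in SAP Table 21. This stands and limits the severity.

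**Stronger readings that the documents do not support.** A reader might infer that the table is bound to show better tolerability for risankizumab. That needs reactions lasting many days and a less reactive dummy. The documents give no duration, Protocol 2.3 calls subcutaneous reactions to risankizumab uncommon, and Protocol 1.2 reports none in the subcutaneous patients of the Phase I trial. A reader might also cite 84 v 7 days at Week 28 and 112 v 21 at Week 44 for patients continuing on risankizumab. Those intervals are arithmetically right, but they are not planned comparisons: in Part B, SAP 11.6 compares local tolerability only among re-randomised patients. Nor are risankizumab reactions wholly unobservable, since Week 1 inspects both actives at 7 days.

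**Conclusion.** The point holds as a timing imbalance in a planned safety comparison. Five of the six planned comparisons inspect active risankizumab later than active adalimumab, and Safety_B_RR has no balanced visit. The intervals follow directly from the schedule and need no assumption.

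The direction of any bias, towards risankizumab, rests on two conditions: reactions fade with time, and saline irritates less than active drug. Its size cannot be derived from the documents. If nearly all reactions clear within 1-2 days, the pre-dose score misses them in both arms, and the fault is insensitivity more than bias. Severity is minor to moderate, with no effect on the primary endpoints, power or alpha.

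**What to change.** **SAP 11.6 (main change).** Limit the between-arm test to Week 1. Report all other pre-dose scores, including Safety_B_RR and the ALL_RZB overall rate, descriptively, labelled with days since last active injection and without Fisher's test. Refer to injection-site adverse events for the comparative statement. This needs no new data and can be done before database lock. The cost is fewer tested visits.

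**Protocol 5.3.5 (optional).** Add post-injection scoring of both products' sites at Visit 2. Both products are injected on site there (Protocol 4.1.4), and the observation period already exists. This gives a second balanced comparison, for patients not yet randomised when it takes effect, at the cost of one short extra inspection. Keep the existing pre-dose inspections.

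Basing the between-arm comparison on fresh BI 655066 sites would not be a remedy. In Part A the adalimumab arm's BI 655066 injections are saline, and its active adalimumab is injected at home from Week 5. Fresh active risankizumab would be set against fresh saline, which reverses the bias. Any post-injection BI 655066 scores at later visits should only describe risankizumab.
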